Various definitions of AKI are used in the literature, but the most widely used are described in the 2012 Kidney Disease Improving Global Outcomes (KDIGO) guidelines [KDIGO, 2012] [see also Section 2.3 Endpoints]. Approximately 2 million major cardiovascular operations are performed globally per year, and AKI occurs often in this subject population. AKI stages 1 to 3 occur in 22.3% and an estimated 1.6% to 5.8% develop AKI that requires dialysis and has an overall mortality of 30% [Hu, 2016]. A large cohort study of 4466 subjects undergoing coronary artery bypass grafting (CABG) and/or valve surgery showed a similar occurrence of AKI: of all AKI 20.1%, and in those with chronic kidney failure (CKD) at baseline, 34.1% were reported to have AKI after surgery [Billings et al, 2016].

Cardiovascular surgery is associated with significant systemic ischemia and reperfusion because of the nature or the surgical processes: clamping of the aorta and the use of cardio-pulmonary bypass pump (CPB) and general low systemic blood flow will cause systemic visceral ischemia, while the restoration of the circulation at the end of the surgery (i.e., when the subject is taken off of the CPB) will induce reperfusion of the ischemic viscera. Various factors contribute to the development of AKI following cardiovascular surgery. These include the use of nephrotoxic agents (e.g., aminoglycoside antibiotics, radio-contrast), renal hypoxia (e.g., catecholamine release, emboli), hemo-dilution, toxins released after blood cell injury (e.g., heme pigments, catalytic iron), oxidative stress, and inflammation [Fuhrman & Kellum, 2017; Thiele et al, 2015].

So far, no specific medical treatment for AKI has been established. Primary treatment of AKI consists of management of blood pressure and cardiac output, which require careful titration of fluids and vasoactive medication. Vasopressors can further reduce blood flow to the tissues if there is insufficient circulating blood volume. Conversely, subjects with AKI are also at increased risk for fluid overload and continued fluid resuscitation despite increased intravascular volume can cause harm. Fluids and vasoactive medications should be managed carefully and in concert with hemodynamic monitoring. Available therapies to manage hypotension include fluids, vasopressors and protocols, which integrate these therapies with hemodynamic goals [KDIGO, 2012].

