    - Urine volume  $< 0.5$  ml/kg per hour for any one of 12 consecutive hours until Visit 6 (i.e., 0-12 hours after T0, 12-24 hours after T0, ..., or 84-96 hours after T0).
19. Severity of AKI within 72 hours after T0
  - Severity of AKI based on AKI-SCr stages (Stage 1, 2, 3 or no AKI. No AKI means subject not developing AKI-SCr72h.)

- Severity of AKI based on AKI-UO stages (Stage 2, 3, or no AKI. No AKI means subject not developing AKI-UO)
- Severity of AKI based on most severe of AKI-SCr or AKI-UO stages (Stage 1, 2, 3 or no AKI)

20. Severity of AKI (based on AKI stage using SCr and/or UO) within 7 days after T0

21. Duration of AKI based on AKI stage using SCr

- Duration of AKI-SCr72h: time from moment of first meeting criteria for AKI-SCr72h until moment of first not meeting the criteria for AKI-SCr72h, death or hospital discharge. If the duration of AKI-SCr72h exceeds day 7 the time of ending of AKI will be assessed retrospectively on day 30 (visit 9) based on local SCr laboratory results. The date and value when respective criteria of AKI-SCr72h were resolved is recorded in the eCRF as an unscheduled event with check of “First NOT meeting the criteria for AKI-SCr72h/7d (SCr  $\geq$ 1.5 times baseline) before hospital discharge, if the duration of AKI-SCr72h/7d exceeds Visit 8 (Day 7).”.
- The duration will be calculated as follows;  
(Date of first not meeting the criteria, death or hospital discharge – Date of first meeting the criteria) in days.  
For subjects who don't occur AKI-SCr72h, the duration of AKI will be treated as 0.
- Duration of AKI-SCr7d (definition as above)

22. Time to AKI-SCr72h (i.e., the time from T0 to the time when criteria for AKI-SCr72h are met). The time to AKI-SCr72h will be calculated as: (Date of first meeting the criteria – Date of T0 + 1) in days.

23. Time to AKI-SCr7d (definition as above)

24. Proportion of subjects with AKI as defined by a 50% or higher reduction in eGFR based on the cystatin-C equation within 72 hours after T0.

- If the subject meet the following condition, then the subject will be treated as with AKI for this endpoint.
  - At least one of eGFR based on cystatin-C equation within 72 hours after T0  $\leq$  50% of the baseline value.

25. Proportion of subjects with AKI as defined by a 50% or higher reduction in eGFR based on the cystatin-C equation within 7 days after T0.

- If the subject meet the following condition, then the subject will be treated as with AKI for this endpoint.

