  - At least one of eGFR based on cystatin-C equation within 7 days after T0  $\leq$  50% of the baseline value.

26. Proportion of subjects that have a reduction of NC AKIRisk score 24 hours after T0 (visit 3) to or below  $0.3 \text{ (ng/ml)}^2/1000$

27. Proportion of subjects with renal recovery, defined as a SCr value at hospital discharge equal to or lower than that at baseline

- SCr value at hospital discharge is defined as follows;

- If the hospital discharge is at or before day 7, the value at Visit 8 will be used.
- If the hospital discharge is after day 7, the value recorded as unscheduled event with check of “Last SCr value before hospital discharge.” will be used.

28. Time to ventilator weaning, defined as the time from T0 to extubation (i.e., removal of the endotracheal ventilation tube)

- Time to ventilator weaning is defined as: (Date and time of Extubation for the first record in “Mechanical Ventilation” form in eCRF – Date and time of T0) in hours.

29. Acute physiology and chronic health evaluation II (APACHE-II) up to day 4 (if the subject is on the ICU)

30. Number of readmissions to ICU

31. Number of readmissions to hospital

- All readmissions after initial hospitalization are included. Initial hospitalization is a hospitalization which includes the day of surgery
- If the date of admission of a hospitalization record is the same as the date of discharge of the previous record, then the two records will be combined into one record.

32. Changes from baseline in SCr, S-cystatin-C, eGFR based on SCr and Cystatin-C, and other biomarkers in blood and urine through 72 hours after T0

33. Area under the curve of SCr and S-cystatin-C through 72 hours after T0 (AUCSCr72h and AUCSCysC72h)

- AUCSCr72h is defined by Linear Trapezoidal Method as below;  
$$\text{AUCSCr72h (mg/dL*day)} = \text{sum of } (SCr_i + SCr_{i+1}) \times (Time_{i+1} - Time_i) / 2$$
where i=Visit 2 to 4
- AUCSCysC72h is defined in the same way as above.
- In the case of missing at 72 hours after T0, the missing value will be imputed from the last available value using Last Observation Carried Forward.

34. Area under the curve of SCr and S-cystatin-C through day 7 after T0(AUCSCr7d and AUCSCysC7d)

- AUCSCr7d and AUCSCysC7d are defined based on all available values through day 7 after T0 in the same way as AUCSCr72h and AUCSCysC72h

35. 5-level European Quality of Life 5 Dimensions Questionnaire (EQ-5D-5L) on baseline, visit 8, day 30 and day 90

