- Mean difference between treatment groups for change from baseline and its 90% CI will be calculated at each visit and t-test will be conducted.
- Mean (+/- SD) plot for the variables and change from baseline will be produced.

Group 5:

- APACHE-II
- SCr, Cystatin-C, eGFR based on SCr and Cystatin-C, kidney injury molecule-1 (KIM1) and AKIRisk Score (For AKIRisk Score, postsurgery value will be used as baseline. If AKIRisk Score at postsurgery is recorded several times in eCRF, the last score will be used as the value at postsurgery.)

The following analysis will be conducted for endpoint group 6.

- Descriptive statistics for the variables will be presented.
- Mean difference between treatment groups for the variables and its 90% CI will be calculated and t-test will be conducted.

Group 6:

- AUCSCr72h
- AUCSCysC72h
- AUCSCr7d
- AUCSCysC7d

The following analysis will be conducted for other endpoints.

- EQ-5D-5L
  - Descriptive statistics for the EQ-5D-5L VAS score and changes from baseline at each visit will be presented for each treatment group. In addition, the descriptive statistics will be presented by subgroups of AKI-SCr72h (Yes/No) and AKI-SCr72h stage 2 or 3 (Yes/No)
  - Mean difference between treatment groups for the EQ-5D-5L VAS and its 90% CI will be calculated and t-test will be conducted.
  - For the EQ-5D-5L qualitative domains, the number and percentage of subjects in each response level value will be reported by visit.
  - Mean (+/- SD) plot for EQ-5D-5L VAS score and change from baseline will be produced.

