### **7.11.2 Outliers**

All values will be included in the analyses.

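### Renal recovery and the end of AKI are judged on serum creatinine alone, so a subject on renal replacement therapy can be scored as recovered or resolved

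*SAP*

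**What the plan says.** In SAP 6.1.3, item 27 analyses the "Proportion of subjects with renal recovery, defined as a SCr value at hospital discharge equal to or lower than that at baseline". The discharge value is chosen by timing only: "If the hospital discharge is at or before day 7, the value at Visit 8 will be used", and for later discharges the last recorded creatinine is taken. Protocol 2.3.3 defines the endpoint the same way.

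Item 21 measures AKI duration as "time from moment of first meeting criteria for AKI-SCr72h until moment of first not meeting the criteria for AKI-SCr72h, death or hospital discharge". When AKI runs past day 7, the eCRF field that records its end also refers only to creatinine against 1.5 times baseline.

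Item 32 covers "Changes from baseline in SCr, S-cystatin-C, eGFR based on SCr and Cystatin-C, and other biomarkers in blood and urine through 72 hours after T0". Items 33 and 34 are trapezoidal AUCs of creatinine and cystatin C to 72 hours and day 7; the only special handling is carry-forward when the 72-hour value is missing. SAP 7.4.4 tests these endpoints between arms. For Group 5, for example: "Mean difference between treatment groups for change from baseline and its 90% CI will be calculated at each visit and t-test will be conducted".

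None of these items mentions RRT, nor does SAP 7.11.1 on missing data. SAP 7.11.2, on outliers, says only: "All values will be included in the analyses". RRT does appear elsewhere. It makes AKI stage 3 in SAP Table 3, is a component of MAKE30 and MAKE90 (SAP 6.1.2), and has its own exploratory endpoints (items 3 and 4).

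**The concern.** RRT removes creatinine from the blood, so a value taken during RRT reflects the therapy as well as the kidney. A rule that looks only at whether creatinine is back to baseline, or below the AKI criterion, cannot tell a recovered kidney from a replaced one.

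At stake is whether the exploratory results mean what their labels say. One subject could appear in the same report as stage 3, as a MAKE event, and as renally recovered. In the continuous endpoints, some of the worst-affected subjects would contribute values that understate their injury, and a real difference between arms in RRT use would be partly masked. If no rule is set beforehand, someone must decide how to treat these subjects after seeing the data.

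**Working it through.** The plan states no figure on this point, so there is none to reproduce. The check has four steps.

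**1. One subject on RRT, by endpoint**

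| Endpoint | What decides it | Subject on RRT with creatinine at baseline |
|---|---|---|
| AKI severity (Table 3; items 19, 20) | creatinine, urine output or start of RRT | stage 3 |
| MAKE30/MAKE90 | death, start of RRT or eGFR | event |
| AKI duration (item 21) | creatinine, death or discharge | AKI ended |
| Renal recovery (item 27) | discharge creatinine | recovered |

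The last two rows contradict the first two.

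**2. Illustrative subject.** All creatinine values are assumed. Baseline is 1.2 mg/dL, so 1.5 times baseline is 1.8. Values are given at baseline, 24, 48 and 72 hours, treated as one day apart. AUC is the sum of (SCr_i + SCr_{i+1}) × 1/2.

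- Severe AKI without RRT (1.2, 2.4, 3.6, 4.8): AUC = (3.6 + 6.0 + 8.4)/2 = 9.0 mg/dL·day; change at 72 h = +3.6.
- RRT after 48 h, 72 h value 1.8: AUC = (3.6 + 6.0 + 5.4)/2 = 7.5; change +0.6; still at the AKI criterion.
- RRT after 48 h, 72 h value 1.2: AUC = (3.6 + 6.0 + 4.8)/2 = 7.2; change 0.0. The value is below 1.8, so AKI ends under item 21. If it is also the discharge value, the subject is recovered under item 27.

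**3. How many subjects.** Protocol 1.1 reports that after cardiovascular surgery "an estimated 1.6% to 5.8% develop AKI that requires dialysis". With 110 per arm:

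- 0.016 × 110 = 1.8 and 0.058 × 110 = 6.4, so about 2 to 6 per arm.
- If these rates rose in proportion to AKI, from the quoted 22.3% to the planned placebo rate of 60% (an assumption): 1.8 × 60/22.3 = 4.7 and 6.4 × 60/22.3 = 17.2.
- Each misclassified subject moves the recovery proportion in that arm by 1/110 = 0.91 percentage points.

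The documents do not say when RRT starts. RRT begun after 72 hours does not touch items 32 and 33.

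**4. Direction between arms.** Suppose one arm has 5 more RRT subjects (AUC 7.5 each), with 110 per arm.

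- Same underlying severity, otherwise undialysed (AUC 9.0): 5 × (7.5 − 9.0)/110 = −0.068. The arm looks better.
- Severe cases in place of stage 1 cases (assumed path 1.2, 1.5, 1.7, 1.7; AUC 4.65): 5 × (7.5 − 4.65)/110 = +0.130. The arm looks worse, but by less than the undialysed course would show: 5 × (9.0 − 4.65)/110 = +0.198.

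In both cases the arm with more RRT is flattered relative to its true kidney function. The sign of the observed difference depends on why RRT differs.

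**The case against.** Much of the case on the other side stands.

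- **Direction.** A reader might infer that the arm with more RRT comes out ahead on these endpoints. The documents do not support that. Values before RRT stay in the AUC, and step 4 shows that the sign can go either way. On duration, subjects without AKI score 0, so a subject with AKI cut short by RRT does not beat one who never had it.
- **Size of the creatinine shift.** A reader might assume that RRT lowers creatinine by 1.0 to 2.5 mg/dL and that the arms differ by 1 to 4 RRT subjects. The mean difference then shifts by 1 × 1.0/110 = 0.009 to 4 × 2.5/110 = 0.091 mg/dL, and the upper figure might be set against the 0.3 mg/dL AKI threshold. Neither input is in the documents. The threshold applies within a subject, so it says nothing about a difference between arm means.
- **Cystatin C.** Nothing in either document says that RRT lowers it. The point rests on creatinine.
- **The all-values sentence.** It sits under Outliers and is not a considered rule for values taken on RRT. The fault is the missing condition in items 21 and 27, not that sentence.
- **RRT is captured elsewhere.** A benefit in fewer RRT starts can be read from MAKE, items 3 and 4, and AKI stage. This limits the harm but does not make the recovery and duration labels correct.

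**Conclusion.** The point holds as a classification error in items 27 and 21. Followed as written, the SAP can score a subject on RRT as recovered, or as having AKI that has ended, while Table 3 and MAKE treat the same subject as stage 3 and an event. For creatinine, creatinine-based eGFR change and AUCSCr (items 32 to 34; Groups 5 and 6), values taken on RRT understate injury. The comparison is biased towards the arm with more RRT relative to its true kidney function; no more than that can be said about direction.

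The firm measure of size is 0.9 percentage points of recovery per misclassified subject. The 2 to 6 RRT subjects per arm rest on applying the protocol's background rate to this trial, and not all of them need be misclassified. The size of any creatinine shift, and any effect on cystatin C, are assumptions.

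All affected endpoints are exploratory. The primary endpoint counts a subject once the criterion is met at any evaluation visit, so a later fall on RRT does not undo it. MAKE counts RRT directly, and the sample size does not depend on these items. The change is worth making before unblinding, but it would not alter the trial's main conclusion.

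**What to change.** Amend SAP 6.1.3 and 7.4.4 before unblinding:

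- **Item 27.** Count a subject as not recovered if RRT was started and is not documented as stopped by discharge, or if the discharge creatinine was taken during RRT.
- **Item 21.** AKI does not end while RRT continues. If no stop date is recorded, treat RRT as continuing to discharge or death.
- **Items 32 to 34, Groups 5 and 6.** Keep the as-observed analysis. Add a pre-specified sensitivity analysis that gives subjects with RRT in the relevant window the worst rank, compared by a rank test such as the Wilcoxon test already planned for Group 2. Cystatin C can follow the same rule for consistency, without claiming that RRT lowers it.

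Do not carry forward the last value before RRT. If RRT starts before Visit 3, the last scheduled value is baseline. On the illustrative path this gives a change of 0 and an AUC of 1.2 × 3 = 3.6, so a very sick subject is scored as uninjured. If RRT starts after 48 hours, it gives (3.6 + 6.0 + 7.2)/2 = 8.4 against 9.0.

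The cost is SAP wording and programming: one further data-handling rule for a few subjects. One thing must be confirmed. SAP Table 1 (footnote 13) collects RRT data and Protocol 5.1.5 mentions the start of RRT, but neither document mentions a stop date. Check that the eCRF records both start and stop.

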#### Follow up

It is assumed that the subjects will be in the hospital up to at least 1 week after the surgery. On days 5, 6 and 7 after T0 (visits 6, 7 and 8, respectively), applicable assessments will be performed to assess study endpoints, including AKI (based on SCr). After end of all the procedures of visit 5, subjects can be discharged at the discretion of the investigator. If the subject is discharged before day 7, visit 8 will be done on the day of discharge and no site visits are required after discharge up to day 7. If the subject is discharged after day 7, visit 8 will be done on day 7 and no additional assessments are required after day 7 up to discharge, but the last result of SCr before discharge from local laboratory testing will be collected. Following day 7 (visit 8) or discharge, subjects will be followed up on day 30 (visit 9) and 90 (visit 10) following surgery. On visits 9 and 10 a composite endpoint of major adverse

kidney events (MAKE), including all-cause mortality, RRT and/or  $\geq 25\%$  sustained reduction in eGFR will be assessed.

Total number of hospital days and ICU days during initial hospitalization will be recorded. If the subjects are readmitted to hospital for any reason during the 90 follow-up days, the total number of hospitalizations and number of days hospitalized through day 30 and 90 will be recorded.

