2. During surgery, the following data have to be assessed in the electronic case report form (eCRF): Procedures (coronary artery bypass graft surgery and/or valve surgery, thoracic aortic surgery, extracorporeal membrane oxygenation, use of ventricular assist device, redo cardiac surgery) and duration of CPB; lowest intraoperative mean arterial pressure; perioperative fluid balance and medication (fluid intake, UO, blood products, drain output, blood loss, inotropics/vasopressors and furosemide); time of incision and closing of skin; T0 and perioperative complications.
3. If the subject is discharged from hospital before day 7, visit 8 will be done on the day of discharge and no site visits are required after discharge up to day 7. If discharged after day 7, no additional assessments are required after day 7 up to discharge except for the recording serum creatinine (SCr) from local laboratory testing.
4. At days 30 and 90, only body weight needs to be measured. A full physical examination is not required.
5. Subjects will only be randomized if postoperative NephroCheck® (NC) AKIRisk® score (assessed between 2 to 22 hours after T0) is  $> 0.3$  (ng/mL) $^2/1000$ . If the AKIRisk score is  $\leq 0.3$  (ng/mL) $^2/1000$ , the subject cannot be randomized and will be followed up in the observational arm, see Schedule of Assessments [[Table 2](#)].  
NC measurements at visits 3, 4 and 5 do not have to be performed at sites: urine samples at visits 3, 4 and 5 will be taken, but frozen until later assessment at central lab.
6. Safety central laboratory tests including serum creatinine (SCr) and cystatin C.
7. If the subject is discharged from hospital after day 7, the last result of SCr before discharge from local laboratory testing will be collected.
8. UO assessment: from T0 (visit 2) to T72 (visit 5) when the subject is in the ICU, UO will be recorded every 12 hours and fluid intake will be recorded every 24 hours. The eCRF should indicate when UO data have to be recorded from the subject ICU record. During the first 72 hours following surgery (i.e., visits 3 to 5), the investigator will be asked to record information on AKI-UO stages 1 to 3 in the eCRF to assess their occurrence as per investigator discretion. When the subject is discharged from the ICU, but is still in the hospital UO and fluid intake every 24 hours will be recorded up to day 7 (visit 8).
9. Include albuminuria dipstick.

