## **6 ANALYSIS VARIABLES**

The value at presurgery will be used as the baseline unless otherwise specified for each endpoint. In case of missing value at presurgery, the last measurement before surgery will be used as the baseline.

The eGFR(SCr) will be calculated using the GFR estimation equation (2009 CKD-EPI creatinine equation) [KDIGO, 2013]. The subject's age at visit 1 should be used for calculation in this study.

Gender	Serum Creatinine	Equation for Estimating GFR
Female	$\leq 0.7 \text{ mg/dl} (\leq 62 \text{ } \mu\text{mol/l})$	$144 \times (\text{SCr}/0.7)^{-0.329} \times 0.993^{\text{Age}} [\times 1.159 \text{ if black}]$
Female	$> 0.7 \text{ mg/dl} (> 62 \text{ } \mu\text{mol/l})$	$144 \times (\text{SCr}/0.7)^{-1.209} \times 0.993^{\text{Age}} [\times 1.159 \text{ if black}]$
Male	$\leq 0.9 \text{ mg/dl} (\leq 80 \text{ } \mu\text{mol/l})$	$141 \times (\text{SCr}/0.9)^{-0.411} \times 0.993^{\text{Age}} [\times 1.159 \text{ if black}]$
Male	$> 0.9 \text{ mg/dl} (> 80 \text{ } \mu\text{mol/l})$	$141 \times (\text{SCr}/0.9)^{-1.209} \times 0.993^{\text{Age}} [\times 1.159 \text{ if black}]$

GFR: glomerular filtration rate; SCr: serum creatinine

Reference: KDIGO 2012 Clinical Practice Guideline for the Evaluation and Management of Chronic Kidney Disease. Official Journal of the International Society of Nephrology: Kidney International Supplements. 2013;3(1):1-150.

The eGFR(serum cystatin C [SCysC]) will be calculated using the GFR estimation equation (2012 CKD-EPI cystatin C equation) [KDIGO, 2013]. The subject's age at visit 1 should be used for calculation in this study.

Gender	Serum Creatinine	Equation for Estimating GFR
Female	$\leq 0.8 \text{ mg/dl}$	$133 \times (\text{SCysC}/0.8)^{-0.499} \times 0.996^{\text{Age}} \times 0.932$
Female	$> 0.8 \text{ mg/dl}$	$133 \times (\text{SCysC}/0.8)^{-1.328} \times 0.996^{\text{Age}} \times 0.932$
Male	$\leq 0.8 \text{ mg/dl}$	$133 \times (\text{SCysC}/0.8)^{-0.499} \times 0.996^{\text{Age}}$
Male	$> 0.8 \text{ mg/dl}$	$133 \times (\text{SCysC}/0.8)^{-1.328} \times 0.996^{\text{Age}}$

GFR: glomerular filtration rate; SCysC: serum cystatin C

Reference: KDIGO 2012 Clinical Practice Guideline for the Evaluation and Management of Chronic Kidney Disease. Official Journal of the International Society of Nephrology: Kidney International Supplements. 2013;3(1):1-150.

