### 6.1.2 Secondary Efficacy Endpoints

1. Proportion of subjects developing AKI (any stage) based on SCr criteria from the KDIGO guideline within 7 days after T0 (i.e., until Visit 8) (AKI-SCr7d).

[SCr evaluation visit: baseline, Visit 3, 4, 5, 6, 7 and 8 (24 hours, 48 hours, 72 hours after T0, and Day 5, 6 and 7/DoD). If the hospital discharge is earlier than Day 7, then the visits prior to DoD and Visit 8 (DoD) will be used.]

- If the subject meets at least one of the following conditions, then the subject will be treated as developing AKI-SCr7d.
  - Increasing in SCr  $\geq 0.3 \text{ mg/dL}$  within any 48 hours until Visit 8; and/or,
  - Increasing in SCr  $\geq 1.5$  times baseline until Visit 8.

2. Proportion of subjects developing AKI based on all captured criteria from the KDIGO guideline within 72 hours after T0 (AKI-KDIGO72h).

[SCr evaluation visit: baseline, Visit 3, 4 and 5 (24, 48, 72 hours after T0)]

[UO evaluation visit: Visit 3, 4, and 5 (0-12 hours, 12-24 hours, 0-24 hours, ..., and 48-60 hours, 60-72 hours and 48-72 hours after T0)]

- If the subject meets at least one of the following conditions, then the subject will be treated as developing AKI-KDIGO72h.
  - Increasing in SCr  $\geq 0.3$  mg/dL within any 48 hours until Visit 5;
  - Increasing in SCr  $\geq 1.5$  times baseline until Visit 5; and/or,
  - Urine volume  $< 0.5$  ml/kg per hour for any one of 12 consecutive hours until Visit 5 (i.e., 0-12 hours after T0, 12-24 hours after T0, ..., or 60-72 hours after T0).
- 3. Proportion of subjects developing AKI based on all criteria from the KDIGO guideline within 7 days after T0 (AKI-KDIGO7d).

[SCr evaluation visit: baseline, Visit 3, 4, 5, 6, 7 and 8(24 hours, 48 hours, 72 hours after T0, and Day 5, 6 and 7/DoD). If the hospital discharge is earlier than Day 7, then the visits prior to DoD and Visit 8 (DoD) will be used.]

[UO evaluation visit: Visit 3, 4, 5, 6, 7 and 8 (0-12 hours, 12-24 hours, 0-24 hours, ..., and 120-132 hours, 132-144 hours and 120-144 hours after T0). If the hospital discharge is earlier than Day 7, then the visits prior to DoD and Visit 8 (DoD) will be used.]

  - If the subject meets at least one of the following conditions, then the subject will be treated as developing AKI-KDIGO7d.
    - Increasing in SCr  $\geq 0.3$  mg/dL within any 48 hours until Visit 8;
    - Increasing in SCr  $\geq 1.5$  times baseline until Visit 8; and/or,

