**Table 3 Definitions of Stages**

Stage	AKI-SCr	AKI-UO
1	$\geq 1.5$ to $< 2$ times baseline, or Increasing $\geq 0.3$ mg/dL within any 48 hours	(Not used for this study)
2	$\geq 2$ to $< 3$ times baseline	$< 0.5$ mL/kg per hour for over 12 hours
3	$\geq 3$ times baseline, Increase in serum creatinine to $\geq 4.0$ mg/dL, or Initiation of RRT	$< 0.3$ mL/kg per hour for over 24 hours, or Anuria for over 12 hours

AKI-SCr: acute kidney injury based on serum creatinine KDIGO criteria; AKI-UO: acute kidney injury based on urinary output; RRT: renal replacement therapy

KDIGO Clinical Practice Guideline for Acute Kidney Injury. Official Journal of the International Society of Nephrology: Kidney International Supplements. 2012;2(1):1-138.

16. Alternative derivations of proportion of subjects developing AKI using different definitions [Table 3] within 7 days after T0.
17. Proportion of subjects developing AKI (any stage) based on SCr criteria from the KDIGO guideline within 5 days after T0 (i.e., until Visit 6) (AKI-SCr5d).  
[SCr evaluation visit: baseline, Visit 3, 4, 5 and 6 (24 hours, 48 hours, 72 hours after T0, and Day 5). If the hospital discharge is earlier than Day 5, then the visits prior to DoD and Visit 8 (DoD) will be used.]
  - If the subject meets at least one of the following conditions, then the subject will be treated as developing AKI-SCr5d.
    - Increasing in SCr  $\geq 0.3$  mg/dL within any 48 hours until Visit 6; and/or,
    - Increasing in SCr  $\geq 1.5$  times baseline until Visit 6.
18. Proportion of subjects developing AKI based on all criteria from the KDIGO guideline within 5 days after T0 (AKI-KDIGO5d).  
[SCr evaluation visit: baseline, Visit 3, 4, 5 and 6 (24 hours, 48 hours, 72 hours after T0, and Day 5). If the hospital discharge is earlier than Day 5, then the visits prior to DoD and Visit 8 (DoD) will be used.]  
[UO evaluation visit: Visit 3, 4, 5 and 6 (0-12 hours, 12-24 hours, 0-24 hours, ..., and 72-84 hours, 84-96 hours and 72-96 hours after T0). If the hospital discharge is earlier than Day 5, then the visits prior to DoD and Visit 8 (DoD) will be used.]
  - If the subject meets at least one of the following conditions, then the subject will be treated as developing AKI-KDIGO5d.
    - Increasing in SCr  $\geq 0.3$  mg/dL within any 48 hours until Visit 6;
    - Increasing in SCr  $\geq 1.5$  times baseline until Visit 6; and/or,

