### **7.11.3 Visit Windows**

All analyses will be performed based on CRF visit with the following exceptions:

- For the baseline, the value at presurgery will be used as the baseline. However in case of missing value at presurgery, the last measurement before surgery will be used as the baseline.
- For the pharmacodynamic analysis, the data for 2-4 hours postdose at visit 2 which is taken within 1 hour after the administration of study drug will be excluded for analysis.

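### The 7-day creatinine and cystatin C AUCs have no time definition or end rule, so a shorter stay can lower them; the AUC t-test also leaves out baseline

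*SAP*

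**What the plan says.** SAP 6.1.3, item 33, builds the 72-hour AUCs by the trapezoid rule: the mean of two neighbouring values times the gap in Time, over the intervals starting at Visits 2, 3 and 4, in mg/dL·day. It adds a last-observation-carried-forward (LOCF) rule: "In the case of missing at 72 hours after T0, the missing value will be imputed from the last available value". Time is not defined. Item 34 moves to the 7-day measures in one sentence: "AUCSCr7d and AUCSCysC7d are defined based on all available values through day 7 after T0 in the same way as AUCSCr72h and AUCSCysC72h".

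The end of the 7-day window depends on discharge. Protocol 2.2.1 (Follow up) assumes a stay of at least a week but then says: "After end of all the procedures of visit 5, subjects can be discharged at the discretion of the investigator". SAP Table 1, footnote 3, adds: "If the subject is discharged from hospital before day 7, visit 8 will be done on the day of discharge". SAP 7.11.3 (Visit Windows) states: "All analyses will be performed based on CRF visit with the following exceptions"; neither listed exception gives a clock time for an AUC. For the first point of the area, SAP section 6 says: "In case of missing value at presurgery, the last measurement before surgery will be used as the baseline".

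For analysis, SAP 7.4.4 puts all four AUCs in Group 6: mean difference, 90% CI and t-test, with no covariate. Group 5 analyses creatinine and cystatin C as change from baseline.

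**The concern.** An area in mg/dL·day grows with the length of time observed. If Time is the actual sampling time and nothing is added after the last sample, two subjects with the same kidney function get different AUCs because one went home sooner. A smaller AUC is meant to show better kidney function, so the measure would mix renal course with length of stay. Other parts of 6.1.3 are explicit where this one is not. Item 22 computes its interval from dates and item 28 from dates and times. AKI-SCr7d in 6.1.2 has a discharge rule: "If the hospital discharge is earlier than Day 7, then the visits prior to DoD and Visit 8 (DoD) will be used". Item 34 has none.

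The Group 6 question is separate. Baseline creatinine is itself the first point of the area, so baseline and AUC should be positively correlated. A comparison that ignores baseline gives away precision that the collected data could supply.

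**Working it through.** The documents state no AUC value, SD or power for these endpoints, so there is no planned figure to reproduce. The values below are illustrations of the SAP's own formula.

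1. **Time grid.** Visits 3, 4 and 5 are at T0 + 24, 48 and 72 hours. The last urine-output slot for AKI-KDIGO7d in SAP 6.1.2 ends at 144 hours, so Day 7 is taken as T0 + 144 hours, or 6 days.

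2. **Flat creatinine, actual times.** Area = level × days observed. At 1.0 mg/dL: last value at 72 hours, 1.0 × 3 = 3.0 mg/dL·day; last value at 144 hours, 1.0 × 6 = 6.0. At 1.3 mg/dL: discharge at 96 hours, 1.3 × 4 = 5.2; stay to 144 hours, 1.3 × 6 = 7.8. The shorter stay lowers the area by 2.6/7.8 = 33% with no change in kidney function.

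3. **Other rules, same subject.** Take an invented course of 1.0, 1.3, 1.5 and 1.4 at 0, 24, 48 and 72 hours, and 1.2 at discharge at 96 hours. The first three trapezoids are 1.15 + 1.40 + 1.45 = 4.0.
   - Actual times, no carry-forward: 4.0 + 1.3 = 5.3.
   - Carry-forward to 144 hours: 5.3 + 2 × 1.2 = 7.7.
   - Visit 8 placed at nominal Day 7: 4.0 + 3 × 1.3 = 7.9.
   - A subject with the same course who stays to 144 hours at 1.2: 7.7.

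4. **Area divided by observed time.** The flat subject scores 1.0 mg/dL at any length of stay. In step 3, the discharged subject scores 5.3/4 = 1.325 and the one who stays 7.7/6 = 1.283. Most of the stay effect goes, but not all.

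5. **Between-arm shift on the actual-time reading.** Shift ≈ creatinine level × difference in mean observed days. With an assumed level of 1.2 mg/dL, differences of 0, 0.25 and 0.5 day give 0, 1.2 × 0.25 = 0.3, and 1.2 × 0.5 = 0.6 mg/dL·day. The stay differences are assumptions.

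6. **Death before day 7.** Values of 1.0, 1.6 and 2.4 at 0, 24 and 48 hours, then death: 1.3 + 2.0 = 3.3 to the last value. With item 33's 72-hour carry-forward, 3.3 + 2.4 = 5.7. Carried to 144 hours, 3.3 + 4 × 2.4 = 12.9.

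7. **Time of the baseline point.** At flat 1.3 mg/dL with the sample assumed drawn 6 hours before T0, the 72-hour area is 1.3 × 3.25 = 4.225 if the draw time is used and 1.3 × 3 = 3.9 if baseline is placed at T0.

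8. **Precision in Group 6.** Adjusting for baseline multiplies the standard error by about √(1 − r²), where r is the within-arm correlation of baseline and AUC. For assumed r of 0.3, 0.5 and 0.7 the factor is √0.91 = 0.95, √0.75 = 0.87 and √0.51 = 0.71. This equals a t-test with 110/0.91 = 121, 110/0.75 = 147 and 110/0.51 = 216 subjects per arm instead of 110.

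**The case against.** The best reply is that the text is less open than it looks and that little hangs on it. These AUCs are exploratory and are not in the protocol's endpoint list. The protocol expects a stay of at least a week. Group 2 compares hospital days, so a difference in stay would be seen. The Group 6 t-test is valid under randomization, and Group 5 already examines the same markers as change from baseline.

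Much of this stands. A reader might infer that three computations have equal standing: actual times, LOCF to day 7, and Visit 8 at nominal Day 7. The documents do not support that. The LOCF rule names only 72 hours, and a subject discharged early has a Visit 8 value, so no visit is missing. SAP 7.11.3 assigns records to visits and supplies no clock time. Actual times with available values is the natural reading, and it is the one in which stay shortens the area.

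A reader might also infer that renal replacement therapy has been overlooked. Item 34 takes the available values without excluding those on therapy, and such therapy is counted in MAKE30, MAKE90 and stage 3 of SAP Table 3 ("Initiation of RRT"). Whether to censor or rank those subjects is a choice of estimand, not a gap shown here. Nor can it be said that the area simply ends at the last value before death, since item 33's rule would carry it to 72 hours.

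What does not stand is the claim that the point is only taste. Seeing a stay difference in Group 2 does not correct the AUC, and baseline adjustment uses data already collected.

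**Conclusion.** The point holds as a minor one. Items 33 and 34 leave Time and the day-7 end undefined, and on the natural reading a subject discharged early has a smaller 7-day area only because the span is shorter: 3.0 against 6.0 mg/dL·day for flat creatinine of 1.0. LOCF to day 7, or nominal Day 7 for Visit 8, would remove this at flat creatinine, but the text does not clearly provide for either.

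It would go too far to conclude that the treatment comparison is biased. That needs stay to differ by arm, and the documents give neither that difference nor the share leaving before day 7. Large percentages built from one invented creatinine course say nothing about the trial.

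The Group 6 t-test is unbiased. Its loss of precision is expected, but its size rests on a correlation that the documents do not give. The primary and secondary analyses are unaffected, and length of stay does not alter the 72-hour AUCs.

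**What to change.** 1. In items 33 and 34, define Time as actual time from T0, with the baseline value placed at T0.
2. For the 7-day measures, report the AUC divided by observed time (mg/dL for creatinine, mg/L for cystatin C). Add LOCF to T0 + 144 hours as a sensitivity analysis, because time-averaging does not fully remove dependence on when a subject leaves. State how the period after a death before day 7 is handled.
3. In Group 6, replace the t-test with ANCOVA adjusting for the baseline value of the same marker, and report the adjusted mean difference with its 90% CI. The eGFR stratum is optional, since it is calculated from creatinine and largely repeats baseline creatinine.

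The cost is a few sentences, one sensitivity run and one model statement, with no new data. The 7-day result changes unit from mg/dL·day to mg/dL. The change belongs before database lock and unblinding, when the SAP is to be final.
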